SUPPLEMENTARY FILE 1: Study Protocol for Fish oil in knee osteoarthritis: A randomised clinical trial of low dose versus high dose (also known as the FOSTAR study).

[figure not shown]
STUDY DESIGN

The FOSTAR study is a randomised double-blind controlled clinical trial of 200 subjects with symptomatic knee osteoarthritis from three Australian centres (The Queen Elizabeth Hospital, Adelaide, South Australia; Menzies Research Institute, Hobart, Tasmania and Royal North Shore Hospital, Sydney, New South Wales). Participants will be recruited and randomly allocated to either high or low dose fish oil, following completion of a one month run-in period.

All participants will provide written informed consent. The study has been approved by The Queen Elizabeth Hospital, Royal North Shore Hospital and Tasmanian Human Research Ethics Committees. The trial was registered with the Australian New Zealand Clinical Trials Registry (ACTRN 12607000415404) on 19th August 2007.

The proposed flow of subjects through the study is shown in Figure 1.

Figure 1. Flow of subjects through the FOSTAR study

RECRUITMENT

Subjects will be recruited at three centres through patient databases currently held by study

Investigators and direct advertising in local newspapers and Arthritis Australia newsletters.

INCLUSION CRITERIA

The inclusion criteria required (i) age greater than 40 years (ii) clinical knee OA defined using American College of Rheumatology criteria [1] and (iii) VAS knee specific pain score greater than 20mm (0-100mm scale). The knee which is most symptomatic knee, as determined by the participant, will represent the ‘index’ knee for the remainder of the study.

EXCLUSION CRITERIA

Exclusion criteria included (i) dementia or inability to give informed consent, (ii) pregnancy or lactation, (iii) severe knee OA (Grade 3 radiographic joint space narrowing using the Osteoarthritis Research Society International atlas), (iv) planned knee replacement surgery, (v) long-term use (≥ 6 months) of anti-inflammatory dose of fish oil (15mL of oil or ≥ 9 capsules), (vi) presence of inflammatory arthritis and (vii) contra-indications to MRI.

RUN-IN PERIOD

Once volunteers have been screened, they will enter a 4-week pre-randomisation run-in period to exclude participants intolerant to taking liquid oil. All subjects will be instructed to take 15 ml daily of a similarly flavoured oil (citrus flavoured Sunola oil). While the exact contents of this preparation will not be revealed, it will be explained to participants that this preparation is designed to test common aspects of the interventions, but differs from the actual test oil preparations. A standardized instructional video demonstrating a method of taking liquid oil that enhanced tolerability by ‘layering’ on juice will be shown to all participants prior to run-in. Participants will be instructed to take the test oil on juice using the two glass technique [2]. Briefly, one of two shot glasses is filled with fruit juice and the other half filled with juice. The required dose of oil is then measured and layered onto the juice in the half filled glass. Without stirring, the contents are then swallowed in a single gulp. Immediately thereafter, the glass of juice alone is sipped slowly over a period of about 15 seconds. The oil and juice is taken with a meal and not on an empty stomach. Carbonated drinks are avoided. The oil can be taken in divided doses. This method has generally been effective in avoiding a ‘repeating’ fish oil taste.

Patients will be reviewed in the 3rd week after commencing the run-in oil. Subjects who do not attend the appointments or are non-compliant (who consume less than 75% of the oil as assessed by volume) or are intolerant of the oil will not be randomised. The requirements

for the run-in test (and the consequences of failing) will be disclosed to the subjects prior to screening. During this run-in period, subjects will be asked to cease fish oil and glucosamine but will be permitted to take paracetamol for first line analgesia and NSAID (ibuprofen up to 400mg QID if required) for second line analgesia. In our experience about 20% of subjects recommended fish oil fail to establish a pattern of daily ingestion. This period will establish the patient's ability to take a test oil preparation using the recommended oil on juice technique as well as tolerance to and adequacy of rescue analgesia, including, if required, the selected NSAIDs. None of these medications, including the 'run-in' oil will be taken in the week prior to the baseline assessment, when randomisation and commencement of the allocated test preparation will take place. The use of a run-in has been used to improve compliance and retention in RCTs [3]

RANDOMIZATION BY CENTRE

Subjects who satisfy compliance criteria and VAS pain score criteria during the run-in period will be randomised (1:1) to one of the two arms of the RCT. The randomisation will be done centrally at The Queen Elizabeth Hospital in Adelaide by computer generated random numbers and will be stratified by centre.

INTERVENTION

Participants will be randomly allocated to one of two treatment arms:

1. Anti-inflammatory dose of fish oil, 15 ml/day (high dose fish oil)
2. Comparator oil comprising 10% fish oil in sunola oil, 15 ml/day (low dose fish oil)

High dose fish oil contains EPA 18% and DHA 12%, supplying 4.5g EPA+DHA per day. The low dose comparator oil, a blend of fish oil and high oleic sunola oil in a ratio of 1:9, supplies 0.45g EPA + DHA per day, which is equivalent to 1.5 standard 1g fish oil capsule daily. Both oils are flavoured with citrus oils and will be provided in identical dark 500mL bottles. Fish oil is sourced from Berg LipidTech Aalesund, Norway. The oils, blending, masking and bottling is performed by Melrose Health, Victoria, Australia. Study oil bottles will be returned at each study visit and volume of unconsumed oil measured to assess compliance. The presence of fish oil in the comparator will obviate the ethical problem of denying patients n-3 fatty acids that are recommended for cardiovascular health and will also add 'fishy' sensate properties that will militate against unmasking. We have previously shown addition of citrus flavouring to fish oils and vegetable oils achieves masking. The EPA and

DHA dose in the undiluted test fish oil has been shown to have anti-inflammatory effects in a variety of clinical settings, whereas the comparator oil will deliver a dose of fish oil that is well below the minimum amount (10ml/d) that has been associated with anti-inflammatory effects in RCTs. Participants will be provided with paracetamol (500mg) tablets with instructions that they could safely use up to 8 per day.

Participants will undergo assessments at baseline, 6 weeks, 3, 6, 9, 12, 18 and 24 months with interim phone calls to participants to encourage continuing compliance and participation

Dietary and general advice:

Subjects will be instructed to use olive oil based products (spreads, cooking oils, dressings etc), where possible, to minimise variation in consumption of n6 polyunsaturated fatty acids which compete with dietary n3 fatty acids. Written instructions regarding technique for taking the oil and directions for the background diet will be provided. All participants will also be given written information on knee osteoarthritis and generic instructions regarding exercises appropriate for maintaining knee function in OA and general fitness. The package of informed consent and written advice will include information regarding potential unwanted effects of fish oil and paracetamol.

COMPLIANCE

The degree of compliance with test oils will be measured in two ways: (i) calculation of consumed fish oil by count of bottles provided and measurement of oil remaining in returned partly used bottles and (ii) fasting plasma omega-3 fatty acid analysis. These assessments will be undertaken at 3, 6, 12, 18 and 24 months. The plasma fatty acid analysis results will not be available to subjects or investigators till the completion of the study.

OUTCOME MEASURES

Primary outcomes:

1. Pain (WOMAC NRS 3.1 index [4], 10 point numerical scale) at 3, 6, 9, 12 and 24 months (knee specific)
2. Change in knee MRI cartilage volume at 2 yrs.

Secondary outcomes:

1. Disability (WOMAC NRS 3.1 index [4], 10 point numerical scale) at 3, 6, 9, 12 and 24 months (knee specific)

2. Quality of life (AQOL) [5]
3. Analgesic use, measured using a daily diary (NSAID) and paracetamol (pill count at each visit)
4. Change in MRI scores of bone marrow lesions at 2 years
5. Safety assessments/adverse events

In addition to the designated outcome measures, blood pressure, full blood count and electrolytes and liver function testing, presence of comorbidities (eg renal disease, cardiovascular disease, peptic ulcer disease) and a diet questionnaire, DQES V2[6], used to assess n-3 and n-6 fatty acid intake in usual diet, will be assessed at baseline.

As the study will extend over two years in a population at an age at risk for cardiovascular disease and declining bone density, routine investigations will be undertaken at baseline and two years to monitor collateral health effects and risks including:

1. fasting blood lipids
2. low titre c-reactive protein
3. bone mineral density of hip and spine
4. lung spirometry (The Queen Elizabeth Hospital participants only)

The assessment schedule is summarized in Table 1, and data collection forms are presented in Appendix 1.

Table 1. Schedule of assessment for primary and secondary outcome measures

FOSTAR STUDY ASSESSMENTS									
	Enrolment	Randomisation	Treatment						Completion
	Visit 1 (~4 weeks)	Visit 2 (0 weeks)	Visit 3 (3 month)	Visit 4 (6 month)	Visit 5 (9 month)	Visit 6 (12 month)	Visit 7 (18 month)	Visit 8 (24 month)	
Informed Consent for FOSTAR	X								
Medical History	X								
Surgical History	X	X	X	X	X	X	X	X	
OA History		X							
Inclusion/Exclusion Criteria	X	X							
Concomitant medications	X	X	X	X	X	X	X	X	
Physical Exam/Vital Signs	X	X	X	X	X	X	X	X	
Fish Oil Dosing DVD	X	X							
Run-In Fish Oil	X								
Diet information sheet		X							
Exercise information sheet		X							
Osteoarthritis Information sheet		X							
Laboratory testing									
Blood sampling for FBC, CRP, LFT electrolytes and fasting lipids		X					X		X
Blood sampling for serum fatty acids		X	X	X	X	X	X	X	
Imaging									
Knee X-ray	X								
MRI scan		X							X
DEXA scan		X							X
Questionnaires									
WOMAC Questionnaire	X	X	X	X	X	X	X	X	
NRS pain Questionnaire	X	X	X	X	X	X	X	X	
MAPT Questionnaire		X					X		X
AQoL Questionnaire		X	X	X	X	X	X	X	
Diet Questionnaire		X							X
Analgesic Medication		X	X	X	X	X	X	X	
Take-Home Diary	X	X	X	X	X	X	X	X	
Randomisation		X							
Study Fish Oil		X	X	X	X	X	X	X	
Pedometer Readings		X							X

MRI scanning and scoring:

MRI scans will be performed at each of the study centres. MRI will be performed on the most symptomatic knee as determined by the participant, and will represent the 'index'

knee for the remainder of the study. Each participant will have an MRI performed on their 'index' knee at baseline and after 2 years. The 'index' knee will be imaged in the sagittal plane on the same model 1.5T whole-body MR unit using a commercial receive-only extremity coil. The following sequence and parameters will be used: a T1-weighted, fat-suppressed, 3-dimensional gradient recall acquisition in the steady state; flip angle 55 degrees; repetition time 58 msec; echo time 12 msec; field of view 16 cm; 60 partitions; 512 × 192 matrix; one acquisition time 11 minutes, 56 seconds. Sagittal images will be obtained at a partition thickness of 1.5 mm and an in-plane resolution of 0.31 × 0.83 mm (512 × 192 pixels).

The MRI scans will be assessed by a single trained observer. Each participant's baseline and follow-up MRI scans will be scored unpaired with blinding to subject identification and timing of MRI. The volumes of individual cartilage plates (medial tibia, lateral tibia and patella) will be isolated from the total volume by manually drawing disarticulation contours around the cartilage boundaries on a section by section basis. These data will then be resampled by means of bilinear and cubic interpolation (area of 312 mm and 1.5 mm thickness, continuous sections) for the final 3D rendering. The coefficient of variation for this method in our hands is 2.1% to 2.6% [7].

Bone marrow lesions (BMLs) will be assessed on a proton density-weighted fat saturation 2D fast spin echo sequence in the sagittal plane. They will be defined as areas of increased signal adjacent to the subcortical bone at the medial tibial, medial femoral, lateral tibial, lateral femoral, superior patella and inferior patella sites. One trained and blinded observer will score BMLs by measuring the maximum area of the lesion (mm^2) at baseline and follow-up, as previously described [8]. The intraclass correlation coefficient (ICC) in our hands for this method of measurement is 0.97 [8].

Radiographic assessment:

Radiographs will only be used as a screening tool at participant recruitment, and not as an outcome measure. Radiographs of the index knee in the Buckland-Wright view will be taken at baseline, to allow comparison with MRI assessments and as this is putatively the most reproducible technique with regard to non-fluoroscopic positioning [9].

Radiographs will be scored independently by 2 trained observers at each site using a published atlas to classify disease in the tibiofemoral joint. The radiographic features of tibiofemoral

OA will be graded in each compartment on a 4-point scale (0-3) for individual features of osteophytes and joint space narrowing [10]. We have shown previously high degrees of intra-observer and inter-observer reproducibility for agreement on features of OA in the knee with regard to both osteophytes and joint space narrowing [11].

Success of Blinding:

Success of blinding will be assessed by asking the participants the following question:
“If you were asked which oil you were taking during the FOSTAR study would you say? Possible responses: Low dose, comparison oil OR high dose fish oil OR I am not sure which oil I may have been taking”. This will be asked at final visit.

ANALYSIS PLAN

Both intention-to-treat and per protocol analyses will be undertaken. Multiple imputation will be used for missing data. Analyses will be performed using longitudinal mixed model regression. The primary interpretation will be the comparison between the two treatment groups at the end of study.

SAMPLE SIZE CONSIDERATION

Sample sizes of 100 per treatment group were selected based on power calculations for longitudinal (ie repeated data) data with 6 treatment visits, $\alpha = 0.05$, $\beta = 0.2$, an attrition rate of 5% per visit, and a standardised treatment effect at the end of the study of 0.4 (i.e. a medium effect).

WITHDRAWALS

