Have all diary adverse event records been transcribed into the CRFs Adverse Events Section	 

Site Number:

Randomisation Number:

Subject Initials:

Study Selected Knee:

[figure not shown]
PREPARATION FOR NEXT APPOINTMENT			
	YES	NO	
			
Has an appointment been made for the subjects next appointment in 6 months time Details:/...../.....am/pm DD/MM/YYYY			
Has the subject been supplied an IMVS form for fasting bloods prior to next visit			
Has a Visit 6 take home diary been supplied and explained			
Has the subject been issued with a pedometer, had its use explained and been asked to use it for seven consecutive days. Please record details in Pedometer Record			
Has the subject been supplied with analgesic medication for pain relief? Please ensure all details are recorded on the Analgesic Medication Form			

Site Number:

Randomisation Number:

Subject Initials:

Study Selected Knee:

FOSTAR STUDY

Visit 7 (18 months) - TREATMENT

Visit Date.....		  /   /    
		DD / MM / YYYY

ANALGESIC USE		
	YES	NO
Has subject withheld taking anti-inflammatory and analgesic medications prior to appointment If YES, continue with questionnaires. If NO, ask subject to withhold analgesic and inflammatory medications from today and complete questionnaires at home. The questionnaires are then to be returned in pre-paid envelopes.		

QUESTIONNAIRES			
	Supplied YES	Completed YES	Completed NO
WOMAC 			
AQoL I 			
NRS pain			

Site Number:

Randomisation Number:

Subject Initials:

Study Selected Knee:

MEDICAL CHANGES

Has the subject been diagnosed with any NEW medical conditions since their last visit?

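### WOMAC is collected at 18 months, but the pain and disability outcome definitions leave that visit out

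*Supplement*

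**What the plan says.** Four places in the protocol bear on when WOMAC is measured and used.

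- **Outcome Measures.** The primary pain outcome is "Pain (WOMAC NRS 3.1 index [4], 10 point numerical scale) at 3, 6, 9, 12 and 24 months (knee specific"). The first secondary outcome uses the same five times: "Disability (WOMAC NRS 3.1 index [4], 10 point numerical scale) at 3, 6, 9, 12 and 24 months (knee specific").
- **Table 1 and Appendix 1.** The row "WOMAC Questionnaire" in Table 1 is marked at all eight visits, including Visit 7 at 18 months. The table's title says that it schedules the primary and secondary outcomes. The form headed "Visit 7 (18 months) - TREATMENT" lists WOMAC among its questionnaires.
- **Intervention.** The text states: "Participants will undergo assessments at baseline, 6 weeks, 3, 6, 9, 12, 18 and 24 months". The 6-week assessment has no column in Table 1 and no form in Appendix 1.
- **Sample Size Consideration.** 100 per group is based on longitudinal "data with 6 treatment visits", alpha 0.05, beta 0.2, 5% attrition per visit and a standardised effect of 0.4 at the end of the study. The six visits are not named.

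The Analysis Plan calls for a longitudinal mixed model, multiple imputation for missing data, and a primary interpretation at the end of study. It does not say which visits enter either model or how time is modelled.

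**The concern.** Depending on the section, a reader counts five, six or seven post-baseline assessments. For a primary outcome the count should be fixed before the data are seen.

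An analyst who takes the outcome definition literally leaves out a WOMAC assessment that has been collected, and the model then has a 12-month gap just before the time point on which the trial is interpreted. A participant who gave an 18-month score and was then lost would have the 24-month value informed by scores no later than 12 months, although a closer one exists. An analyst who uses the 18-month data departs from the outcome as written. Either choice can be defended from the present text, which is the difficulty.

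**Working it through.** **Side by side: post-baseline times**

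| Place | Times | Count |
|---|---|---|
| Outcome Measures (pain, disability) | 3, 6, 9, 12, 24 months | 5 |
| Table 1 and forms, Visits 3 to 8 | 3, 6, 9, 12, 18, 24 months | 6 |
| Sample Size Consideration | not named | 6 |
| Intervention text | 6 weeks; 3, 6, 9, 12, 18, 24 months | 7 |

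**The protocol's 100 per group.** A plain two-sample comparison (0.4 SD, two-sided 0.05, 80% power) needs 99 per arm, but uses neither the visits nor the attrition. Inflating for six visits of attrition, 99/0.735, gives 135. A mixed model with a group-by-linear-time effect, baseline plus the six scheduled visits and an assumed compound-symmetry correlation of 0.4 gives 99.8. Six equally spaced occasions including baseline give 100.0. So 100 can be reached, but only by assuming a correlation that the protocol does not state, and the match does not show which six visits were meant.

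**Share of observations at 18 months.** Input: 5% loss per visit, 200 randomised, people who are lost stay lost. Retention at post-baseline visit k is 0.95^k.

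- Expected observations at the six visits: 190.0, 180.5, 171.5, 162.9, 154.8, 147.0; total 1,007.
- 18-month share: 154.8 / 1,007 = 15.4%. Without attrition it is 1/6 = 16.7%.
- People with an 18-month but no 24-month value: 200 × (0.7738 − 0.7351) = 7.7.
- New losses by interval: 10.0, 9.5, 9.0, 8.6, 8.1, 7.7; total 53.0 by 24 months.

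**Power for the 24-month contrast, 100 per arm, with and without 18 months.** Let p_k be the proportion whose last observed visit is k, X_k the design rows up to that visit, and V_k their correlation matrix. Per-person information is I = Σ p_k X_k′ V_k⁻¹ X_k. The variance of the group difference is 2 c′(100·I)⁻¹c, and power is Φ(0.4/√variance − 1.96). All correlations are assumptions, because the protocol gives none; serial correlation is per 6 months.

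| Model | Correlation | With 18 m | Without |
|---|---|---|---|
| Visit-specific means | compound symmetry 0.5 | 71.6% | 71.5% |
| Visit-specific means | serial 0.7 | 70.2% | 69.6% |
| Linear effect, zero at baseline | serial 0.8 | 76.5% | 75.8% |
| Linear effect, zero at baseline | compound symmetry 0.5 | 85.8% | 78.9% |
| Linear group-by-time, baseline in model | compound symmetry 0.4 | 80.1% | 72.3% |

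In the last row the required size rises from 99.8 to 120.5 per arm. For the linear effect that is zero at baseline, weaker serial correlation raises the loss a little: at 0.5 it is 74.6% against 72.6%, or 2.0 points.

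**The case against.** The strongest reply is that this is a drafting slip. The Analysis Plan excludes no visit, Table 1 itself presents the 18-month WOMAC as an outcome assessment, and multiple imputation can draw on any collected variable whatever the outcome list says. This stands in part. A reader might infer that the plan discards 15% of its outcome data, but the documents do not say so; that follows only if the outcome list is read as the list of analysed visits.

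Three other strong readings also go beyond the text.

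- **That 18 months was certainly counted in the power calculation.** Visits 3 to 8 are the natural six, since baseline is labelled as the randomisation visit. But baseline plus the five listed times also makes six, as do 6 weeks plus those five, and the forms label Visit 8 as completion rather than treatment.
- **That 15% of observations means 15% of the information.** The primary contrast is at 24 months. With visit-specific means, earlier visits help it only through those who are later lost, so the cost is under 1 point.
- **That the gap falls where losses are heaviest.** Cumulative loss is highest at 24 months, but new losses are smallest between 18 and 24 months (7.7, against 10.0 before the first visit). About 45 of the 53 people missing at 24 months have no 18-month value of their own to contribute.

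The mismatch between the outcome definition and the schedule survives all of these.

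**Conclusion.** The concern holds as an inconsistency that can be corrected at no cost; it is not a flaw in the design. WOMAC is collected at 18 months and both outcome definitions omit it. Read literally, the definitions leave about 15% of expected post-baseline WOMAC observations unused and affect the information available for about 8 people at 24 months; both figures rest on the protocol's 5% loss per visit.

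The effect on the primary comparison runs from under 1 power point (visit-specific means, or a linear effect with serial correlation of 0.7 or more) to about 7 to 8 points (linear effect, compound symmetry of 0.4 to 0.5). The protocol specifies neither the time structure nor the correlation, so it does not settle where in that range the trial lies. Low severity.

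**What to change.** 1. Change the time points in both the pain and the disability definitions to 3, 6, 9, 12, 18 and 24 months.
2. State in the Analysis Plan that all six visits enter the mixed model and the imputation model, that the 24-month contrast remains primary, and how time is modelled.
3. Name the six visits, and the within-person correlation assumed, in the sample size paragraph.
4. Reconcile the 6-week assessment in the Intervention text with Table 1 and the forms, so that all visit lists agree.

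The cost is wording only. The 18-month WOMAC is already scheduled and has a form, so no added visit, participant burden or data collection is involved. The changes should be made before unblinding.

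### Two primary outcomes share one alpha of 0.05 with no testing order, split or success rule, so either the error rate is about 9–10% or the joint power is below 80%

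*Supplement*

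**What the plan says.** Under Primary outcomes the protocol lists two items: WOMAC pain in the study knee, at five time points from 3 to 24 months, and "Change in knee MRI cartilage volume at 2 yrs".

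The Analysis Plan section settles the time point: "The primary interpretation will be the comparison between the two treatment groups at the end of study". On analysis sets it says "Both intention-to-treat and per protocol analyses will be undertaken" and ranks neither above the other.

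The cartilage outcome is worded in the singular. The MRI section says "The volumes of individual cartilage plates (medial tibia, lateral tibia and patella) will be isolated from the total volume" but does not say whether the outcome analysed is one plate, a sum or a total.

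The Sample Size Consideration section gives the only error rates in the document: alpha 0.05 and beta 0.2, for a standardised effect of 0.4 at the end of the study, with 100 per group and "an attrition rate of 5% per visit". It does not say which primary outcome these figures describe. No section gives an alpha allocation, a testing order, a multiplicity adjustment or a rule for declaring the trial positive.

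**The concern.** With two primary outcomes and one alpha, a reader cannot tell what error rate attaches to the trial's main conclusion. Pain and cartilage structure may not move together. If one reaches significance and the other does not, the plan gives no rule for the headline result, and the decision would be made after the results are seen. The unnamed cartilage measure and the two unranked analysis sets leave further room for choice at that stage.

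**Working it through.** **Inputs from the protocol.** Two primary outcomes; alpha 0.05; beta 0.2; standardised effect 0.4; 100 per group; 1:1 allocation; 5% attrition per visit over 6 treatment visits. Sidedness is not stated, so two-sided is assumed. Correlations between outcomes are not given, so a range is shown.

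**Step 1: the plan's own sample size.** For a simple two-group comparison, n per group = 2 × (1.960 + 0.842)² / 0.4² = 98.1, rounded up to 99. Power at 100 per group is 80.7%. The planned 100 therefore matches one two-sided test at an unsplit 0.05, before attrition and without using repeated measures. A one-sided test would need 78. The longitudinal calculation itself cannot be checked, because its within-person correlation is not reported.

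**Step 2: if either outcome suffices, each at 0.05.** If independent, the error is 1 − 0.95² = 0.0975. For correlated test statistics (bivariate normal, both tails):

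| Correlation | Chance of at least one false positive |
|---|---|
| 0 | 9.75% |
| 0.3 | 9.5% |
| 0.5 | 9.1% |
| 0.7 | 8.3% |

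These figures count both directions. For false claims of benefit alone, the independent case is 1 − 0.975² = 4.9%, against 2.5% for one test, so the ratio is again about two.

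**Step 3: if both outcomes must succeed.** The error is at most 5%. With 80% power for each, joint power is 0.8 × 0.8 = 64% if the two are independent. At correlation 0.5 it is 69% (both statistics exceeding their critical values, bivariate normal). It reaches 80% only if the two tests are perfectly correlated.

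**Step 4: if each cartilage plate were tested separately.** This is conditional, because the plan does not say so. Pain plus three plates, each at 0.05, gives 1 − 0.95⁴ = 18.5% if all are independent. By simulation it gives about 17% with plates correlated 0.5 and about 15% with plates correlated 0.7.

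**Step 5: two analysis sets.** For one outcome, counting a success in either intention-to-treat or per protocol gives 6.4% to 8.1%, over assumed correlations of 0.95 to 0.75 between the two analyses. The addition is modest.

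**Step 6: the power cost of testing pain at 0.025.** This is what pain faces under Hochberg when cartilage is not significant at 0.05. Retention over 6 visits is 0.95⁶ = 73.5%, or 73.5 per arm. With an assumed baseline correlation of 0.5, the effective effect size is 0.4 / √(1 − 0.5²) = 0.462. Two-sample t-test power is 79.4% at 0.05 and 70.3% at 0.025.

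Other assumptions give a similar cost. At 100 per arm with no attrition and no baseline adjustment, power falls from 80.7% to 72.1%. At 73.5 per arm with no baseline adjustment, it falls from 67.9% to 57.3%. The cost is about 9 to 11 points.

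**The case against.** The strongest reply is that the plan never says one success is enough. Alpha 0.05 appears only in the sample size section, no familywise rate is claimed, and inflation follows only from an either-can-win rule that is not written down. If both outcomes were required, the error would not exceed 5%. If pain and structure are read as two separate questions, the need for a joint correction is debated. All of this is fair, and it means the defect is an unspecified rule rather than a stated error. It does not remove the problem: under one reading the error is about double, and under the other the joint power is below the planned 80%.

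A reader might also infer that every plate and both analysis sets are tested at 0.05 as separate routes to success, and so take the error to be 15–19% or higher. The documents do not support that. The cartilage outcome is singular, the plate sentence describes image segmentation, and reporting both analysis sets is ordinary practice. The Withdrawals section also keeps participants in follow-up after they stop the study oil, which suits an intention-to-treat analysis.

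Finally, no separate SAP is shown, and the choice of plate and confirmatory set is commonly left to one. Those two points are therefore clarifications. The success rule is harder to defer, because the sample size in this protocol depends on it.

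**Conclusion.** The concern holds in this form: two primary outcomes, one alpha, and no order, split or success rule. If either can carry the trial at two-sided 0.05, the familywise error is about 9–10% for correlations from 0 to 0.5. If both must succeed, joint power is 64% when they are independent with 80% each, and below 80% short of perfect correlation. The two-outcome error figure needs no assumption about plates or analysis sets. The unnamed cartilage measure and the unranked analysis sets are secondary gaps that leave room for choice after the results. The 15–19% range would apply only if each plate were tested separately, which the plan does not state. Visits add no multiplicity for pain, because the end-of-study sentence fixes the comparison.

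**What to change.** Add a few sentences to the Analysis Plan section:

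- **Control the two primary outcomes at 5% overall by one of two routes.** A fixed order, with pain at 24 months first and cartilage second, keeps 0.05 for pain and leaves the sample size unchanged. Its cost is that cartilage is confirmatory only if pain succeeds. Hochberg lets either outcome succeed alone. Its cost is power when only one shows an effect: for pain, about 79% falls to 70% under the assumptions in Step 6.
- **Name one cartilage measure in advance** and make the others secondary. The choice among a total, a sum or a single plate belongs to the investigators, but it should be fixed before unblinding.
- **State that the intention-to-treat comparison at 24 months is confirmatory** and that per protocol is supportive.
- **Say which primary outcome the power statement describes**, so that alpha and beta attach to a named test.

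None of this changes data collection.

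### The one sample-size calculation rests on six repeated visits and does not carry over to the cartilage-volume primary outcome, which has a single follow-up scan

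*Supplement*

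**What the plan says.** Under OUTCOME MEASURES the protocol lists two primary outcomes. The first is WOMAC pain, recorded at several visits. The second is "Change in knee MRI cartilage volume at 2 yrs".

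SAMPLE SIZE CONSIDERATION is one paragraph and names no outcome. It reads: "Sample sizes of 100 per treatment group were selected based on power calculations for longitudinal (ie repeated data) data with 6 treatment visits". Its other inputs are alpha 0.05, beta 0.2, a 5% loss at each visit, and a final-visit effect of 0.4 SD, which it calls medium.

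Under MRI scanning and scoring, the index knee is imaged in each participant's "knee at baseline and after 2 years". Table 1 shows the same two scans.

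ANALYSIS PLAN calls for longitudinal mixed models and multiple imputation, and adds: "The primary interpretation will be the comparison between the two treatment groups at the end of study". It names no baseline covariate and no imputation model. No effect, SD of change or power is given for cartilage anywhere in the protocol.

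**The concern.** A power calculation for repeated data draws on several measurements per person. With such data, someone who leaves after a year has still contributed several pain scores. Cartilage change has no such reserve: a person without the 24-month scan contributes no change value at all. Planned attrition therefore falls in full on this outcome.

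The paragraph justifies the size of a trial with two primary outcomes and excludes neither, so a reader will naturally apply beta 0.2 to both. A null cartilage result would then be read as having had a 20% chance of missing the planned effect. On the protocol's own effect and attrition figures, that chance is nearer 30-33%.

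**Working it through.** **Inputs.** From SAMPLE SIZE CONSIDERATION: 100 per arm, alpha 0.05, beta 0.2, effect d = 0.4 SD, 6 treatment visits, 5% loss per visit. From RANDOMIZATION BY CENTRE: 1:1 allocation. From MRI scanning and scoring: one follow-up scan. Assumed here: a two-sided test (sidedness is not stated), no baseline adjustment, nothing regained by imputation, and d = 0.4 expressed in SDs of cartilage change.

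**1. The protocol's own figure.** The 100 per arm cannot be derived from the stated inputs alone, because neither the within-person correlation nor the tested contrast is given. Two quite different routes arrive near it:
- A single two-sample t test at d = 0.4 with no loss needs 99.1 per arm; 100 per arm gives 80.4% power.
- A mixed model with linear time and a group-by-time term estimates the 24-month difference from visits at 3, 6, 9, 12, 18 and 24 months. With an assumed compound-symmetry correlation of 0.6, no baseline term and six losses of 5%, it needs 99.8 per arm (80.1% power at 100).

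**2. Number scanned at 24 months.**
- Six losses, compounded: 100 × 0.95^6 = 73.5 per arm.
- Five losses (none before the first treatment visit): 100 × 0.95^5 = 77.4 per arm.
- Additive readings: 100 × (1 − 0.25) = 75 and 100 × (1 − 0.30) = 70 per arm.

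**3. Power for one comparison at 2 years.** Noncentral t with 2n − 2 degrees of freedom and noncentrality d × √(n/2). For n = 73.5 this is 0.4 × √36.75 = 2.42; for n = 100 it is 0.4 × √50 = 2.83. The last column is the effect that gives 80% power at that n.

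| Scanned per arm | Power at 0.4 SD | Effect at 80% power |
|---|---|---|
| 100 (no loss) | 80.4% | 0.398 SD |
| 77.4 | 69.6% | 0.453 SD |
| 75 | 68.2% | 0.460 SD |
| 73.5 | 67.3% | 0.465 SD |
| 70 | 65.2% | 0.477 SD |

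The normal approximation gives 70.1% and 67.9% for 77.4 and 73.5 per arm.

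**4. Where the shortfall comes from.** The first row shows that losing the repeats alone would leave power at 80.4%. The loss comes from attrition at a single time point, which no intermediate scan can offset. Holding 80% power at 0.4 SD would take 99.1 / 0.774 = 128 to 99.1 / 0.735 = 135 randomised per arm.

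**5. What baseline adjustment could restore.** A baseline covariate with correlation ρ to the analysed outcome multiplies the required number by (1 − ρ²). To get back to 80%, ρ must be √(1 − 77.4/99.1) = 0.47 to √(1 − 73.5/99.1) = 0.51.

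**The case against.** The strongest reply is that the paragraph describes repeated data and so on its face concerns pain. It never claims 80% power, or an effect of 0.4 SD, for cartilage. This stands in part. A reader might infer that cartilage power simply is 67-70%. The documents do not support that: with no expected effect and no SD of cartilage change, the power is undetermined, and 67-70% is what follows if 0.4 SD is carried across. But if the paragraph covers pain only, one of the two primary outcomes has no power statement, and the protocol still needs the missing line.

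A second reply is that information can be regained. Baseline scans exist, multiple imputation is planned, and WITHDRAWALS says participants are followed after stopping the oil. Each could help. However, no covariate, correlation or imputation model is stated, so the protocol cannot count on the gain, and "an attrition rate of 5% per visit" is its own planning figure. Were only 5% lost in total, power would be 78.3%.

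Two further inferences are tempting and should not be drawn:
- **That attrition was ignored, because 100 is close to 99.1.** The linear-time model in the working also arrives at 100 per arm with attrition included, so the match proves nothing.
- **That pain at 24 months is below 80% unless baseline pain is adjusted for.** A model with a separate group difference at each visit and no baseline term gives about 68-79% over assumed correlations of 0.3-0.9. The linear-time model at compound-symmetry correlations of 0.5-0.6 gives 80-83% with the stated attrition. The protocol fixes neither contrast nor correlation, so no pain shortfall can be asserted.

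**Conclusion.** The point holds in a limited form. A calculation built on six repeated visits gives no assurance for an outcome with one follow-up scan, and the protocol offers nothing else for cartilage volume. If the 0.4 SD effect and 5% loss per visit are applied to cartilage change, unadjusted power at two-sided 0.05 is about 67-70%, or 65-70% across readings of the attrition. The effect detectable with 80% power is about 0.45-0.47 SD (0.48 SD at 30% loss). The figures assume no baseline adjustment and no recovery through imputation. This is a gap in the sample-size justification for one primary outcome. It does not show that 100 per arm is wrong for pain.

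**What to change.** In SAMPLE SIZE CONSIDERATION:

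1. Say that the 80% figure refers to the repeated pain outcome, after the sponsor has confirmed this against the calculation that was run.
2. Add a separate line for cartilage volume giving the expected number scanned at 24 months, the assumed effect in SDs of change, any baseline adjustment, and the resulting power. On the present inputs, without adjustment, it would read: about 73-77 per arm scanned; power 67-70% at 0.4 SD; 80% power at about 0.45-0.47 SD. If a baseline covariate is to be used, name it and state the assumed correlation before claiming a higher figure.
3. State that a null cartilage result will be read against that detectable effect and not against beta 0.2 at 0.4 SD.

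This changes wording only, with no added enrolment and no change to conduct. The cost is that the stated power becomes less favourable for one of the two primary outcomes.
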